### **Sample size calculations**

Sample size calculations were derived using Stata 16 and are based on the Self-Report Delinquency Scale (Smith and McVie, 2003). This measure has 18 two-part questions that measure the number of different offences committed, and the volume of offences committed

over a fixed period. We are interested in the latter outcome over a six-month period. The scale has good psychometric properties (Fonagy et al., 2018, Humayun et al., 2017) and correlates well with official police charges ( $R = 0.95$ ; (McAra and McVie, 2007)).

We have used an effect size difference of 0.25 as an important difference; this equates to a difference in volume of offences of circa 12% over a 6-month period, similar effects as found in other psychologically focussed interventions to reduce recidivism in adolescent populations (Hodgkinson et al., 2021). To detect this difference or greater, using a two-sided test, alpha of 0.05 and power at 80% requires 506 young people to be followed-up at our primary endpoint, 6-months post-randomisation, 253 in each group. There is no reliable literature on pre- and post-test correlations for the SRDS, so we have erred on the side of caution and not accounted for this in the sample size calculation as an incorrect assumption increases the risk of an under-powered trial. If we take a potential loss to follow-up of 10%, similar to attrition found in our other studies of young people (Coulton S et al., 2023), this inflates the required baseline sample to 562. We have 80 potential interventionists, 40 randomised to each arm. Each interventionist can manage a harmonic mean of 10 young people through the course of the study. To achieve our target, we would need to have at least 56 of these interventionists participating throughout the trial, 28 in each arm, thus allowing for a potential loss of interventionists of 24, 30% of those available.

Assuming only 80% of young people approached consent to take part, as found in similar studies (Coulton S et al., 2023), means we would need to approach 702 young people, over the recruitment period. Allowing for a slower start of 20/ per month recruited over the first three months, means 36 will need to be recruited in each month between January 2024 and February 2025, allowing for a six-month follow-up for the interim report submitted in September 2025.

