### **Primary outcome**

Self-reported delinquency will be assessed using the Self-Report Delinquency Scale (SRDS; (Smith and McVie, 2003)) over the previous six months. This 19-item questionnaire has established psychometric properties (Fonagy et al., 2018) in this population and has a strong correlation ( $R=0.95$ ) with police charges (McAra and McVie, 2007). This outcome will be assessed at baseline, 6- and 12-months post randomisation. As the funder requires a final report by September 2025, the 6-month post-randomisation time-point will be the primary endpoint.

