Secondary outcome and data source	
Young Person:
 
Number of delinquent offences in the past 12 months derived from the SRDS at months 6 and 12.
 
Self-report behaviour and personality attributes (overall emotional and behavioural difficulties, emotional symptoms, conduct problems, hyperactivity, peer relationships, prosocial behaviour, externalising behaviours, internalising behaviours) derived from the Strengths and Difficulties Questionnaire (SDQ) at month 6 and 12.
 
Self-report non-psychotic mental health derived from the General Health Questionnaire (GHQ12) at months 6 and 12.
 
Self-report wellbeing derived from the Short Warwick Edinburgh Mental Wellbeing Scale (SWEMWBS) at month 6 and 12.
 
Self-report family cohesion, expressiveness and conflict derived from the Brief Family Relationship Scale (BFRS) at month 6 and 12.
 
Self-report Client Service Receipt Inventory (CSRI) to assess police involvement at month 6 and 12 (arrests, cautions, charges, court attendance), educational outcomes (suspensions, exclusions, managed moves) and employment status.
 
Staff
 
Self-report Attitudes Related to Trauma Informed Care

	
(ARTIC) measured before training, and at month 6 and 12 after training.
 
Self-report Short Warwick Edinburgh Mental Wellbeing Scale (SWEMWBS) before training and at month 6 and 12 after training.
 
Staff turnover throughout the trial and staff absence throughout the study period.

--	--

SAP version history

Version	Date	Changes made and reason for revision
1.0 [original]		

Table of contents

Introduction 5

Intervention 6

Design overview 9

Sample size calculations overview 12

Analysis 13

Introduction

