	measure (instrument, scale, source)	
Participants
 
Self-Report delinquency Scale (SRDS), Strengths and Difficulties Questionnaire (SDQ), General Health Questionnaire (GHQ12), Short Warwick Edinburgh Mental Wellbeing Scale (SWEMWBS), Brief Family Relationship Scale (BFRS), Client Service Receipt Inventory (CSRI),
 
Staff
 
Attitudes related to Trauma Informed Care (ARTIC), Short Warwick Edinburgh Mental Wellbeing Scale (SWEMWBS), Staff records.

Sample size calculations overview

		Protocol
Minimum Detectable Effect Size (MDES)		0.25
Pre-test/ post-test correlations	level 1 (participant)	n/a
	level 2 (cluster)	n/a
Intracluster correlations (ICCs)	level 1 (participant)	n/a
	level 3 (cluster)	n/a
Alpha		0.05
Power		0.8
One-sided or two-sided?		Two-sided
Average cluster size		n/a
Number of clusters	intervention	n/a
	control	n/a
	total	n/a
Number of participants	intervention	253
	control	253
	total	506 (562 allowing for 10% attrition at month 6)

Sample size calculations were derived using Stata 16 and are based on the Self-Report Delinquency Scale (Smith and McVie, 2003). This measure has 18 two-part questions that measure the number of different offences committed, and the volume of offences committed over a fixed period. We are interested in the latter outcome over a six-month period. The scale has good psychometric properties (Fonagy et al., 2018, Humayun et al., 2017) and correlates well with official police charges ($R = 0.95$; (McAra and McVie, 2007)).

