We have used an effect size difference of 0.25 as an important difference; this equates to a difference in volume of offences of circa 12% over a 6-month period, similar effects as found in other psychologically focussed interventions to reduce recidivism in adolescent populations (Hodgkinson et al., 2021). To detect this difference or greater, using a two-sided test, alpha of 0.05 and power at 80% requires 506 young people to be followed-up at our primary endpoint, 6-months post-randomisation, 253 in each group. There is no reliable literature on pre- and post-test correlations for the SRDS, so we have erred on the side of caution and not accounted for this in the sample size calculation as an incorrect assumption increases the risk of an under-powered trial. If we take a potential loss to follow-up of 10%, similar to attrition found in our other studies of young people (Coulton S et al., 2023) this inflates the required baseline sample to 562. We have 73 potential interventionists, 35 randomised to control and 36 randomised to be trained in the intervention delivery. Each interventionist can manage a harmonic mean of 10 young people through the course of the study. To achieve our target, we would need to have at least 56 of these interventionists participating throughout the trial, 28 in each arm, thus allowing for a potential loss of interventionists of 17, 23% of those available.

Assuming only 80% of young people approached consent to take part as found in similar studies (Coulton S et al., 2023) means we would need to approach 702 young people, over the recruitment period. Allowing for a slower start of 20/ per month recruited over the first three months, means 36 will need to be recruited in each month between January 2024 and February 2025, allowing for a six-month follow-up for the interim report submitted in September 2025.

Analysis

All analysis is conducted using STATA 16 SE. Analysis will be conducted and presented in accordance with the CONSORT guidelines. The validity of randomisation will be explored by presenting baseline measures of central tendency and estimates of precision for continuous variables, and proportions for categorical variables broken down by allocated arm and stratification factors for both staff and participant samples.

Primary outcome analysis

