The primary outcome relates to the participant and is the quantity of self-reported delinquent acts in the six months after randomisation assessed using the SRDS. The quantity of delinquent acts is calculated as the sum of positive endorsements for each of the nineteen questions in the SRDS. Two datasets will be created for statistical analysis, the primary analysis will be based on the intention to treat (ITT) dataset. The secondary analyses will examine intervention effects under different scenarios for compliance with allocation (see compliance section below): complier average causal effects (CACE); and per protocol (PP).

The ITT dataset contains all available data for participants who were randomised, regardless of whether they complied with allocation. This dataset will include participants who were withdrawn/withdrew from the trial post-randomisation. These analyses are a lower bound estimate of intervention effects as they represent the effect of offering an intervention, rather than the effect of receiving the intervention.

The primary outcome is the quantity of offences at 6-months post-randomisation. We expect the primary outcome will take the form of a linear distribution. Prior to analysis we will conduct a series of diagnostic tests and assess the underlying assumptions prior to choosing an appropriate and statistically rigorous regression approach. The analysis will take the form of an analysis of covariance using a linear regression. Models will be adjusted by baseline values, quantity of offences in the six months prior to randomisation and stratification factors, service, age group and sex, as covariates. The regression model specification is as follows (eq.1):

$$SRDS6_{i,j} = \alpha + \beta_1(allocation)_{i,j} + \beta_2(SRDS0)_{i,j} + \beta_3(sex)_{i,j} + \beta_4(age)_{i,j} + \beta_5(service)_j + \varepsilon_i$$

Where for participant i within service j ; $SRDS6$ is the 6-month SRDS score, $allocation$ is the allocated group, $SRDS0$ is the baseline SRDS score, sex is the participant sex, age the age group, $service$ the service level dummy variables to adjust for fixed effects and ε_i the individual level error.

An estimate of difference will be generated as a mean difference between the groups and the associated 95% confidence interval.

Secondary outcome analysis

For participants the quantity of offences reported at 12-months will be analysed using similar methods as 6-months (eq. 2).

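### The SAP's scoring rule makes the primary outcome a count of offence types, while both documents state the outcome and its target difference as volume of offences

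*SAP*

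**What the plan says.** **Scoring rule.** SAP, Primary outcome analysis: "The quantity of delinquent acts is calculated as the sum of positive endorsements for each of the nineteen questions in the SRDS". Equation 1 calls its dependent variable only the 6-month SRDS score. No other scoring rule appears in either document.

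**Outcome of interest.** Protocol, Sample size calculations: "This measure has 18 two-part questions that measure the number of different offences committed, and the volume of offences committed" over a fixed period. The SAP's Sample size calculations overview repeats this and continues: "We are interested in the latter outcome over a six-month period". The latter is volume.

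**Target difference.** SAP, same section: "We have used an effect size difference of 0.25 as an important difference", followed by "this equates to a difference in volume of offences of circa 12% over a 6-month period". No mean or SD is given.

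**Labels elsewhere.** The summary tables of both documents define the primary outcome as a number of offences in the past six months at month 6. The protocol's Analysis section uses a mean difference in number of offences over the six months from baseline.

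**Item count.** The sample size sections say 18 two-part questions. The protocol's Primary outcome section says "This 19-item questionnaire has established psychometric properties", and the SAP's scoring rule agrees with that count. The tables of measures (protocol Table 3; SAP, Longitudinal follow-up analyses) list 36 items.

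**Secondary SRDS outcome.** Both summary tables list: "Number of delinquent offences in the past 12 months derived from the SRDS at months 6 and 12". The design tables list an SRDS secondary at 12 months only, equation 2 models month 12 only, and the protocol's Primary outcome section describes a six-month look-back at every assessment.

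**The concern.** Endorsing a question records that a type of offence occurred. How often it occurred is the other part of the question, and that part does not enter the rule. Two young people who report the same single offence type, one once and one many times, both score 1. An intervention that makes an offence rarer without stopping it would leave the score unchanged.

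A programmer working from the SAP would therefore build the quantity that the sample size section names and then sets aside. The trial would report an effect on the range of offending under a label that readers will take as the amount of offending, and its result could not be compared with the 12% target. Changing the score after results are known would look like outcome switching.

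**Working it through.** **1. The plan's own figure.** Inputs from the sample size sections: d = 0.25, two-sided alpha 0.05, power 80%, equal arms.

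- Normal approximation: n per arm = 2(1.960 + 0.842)² / 0.25² = 251.2, so 252.
- t-test version: 252.13, so 253 per arm and **506** in total, as stated. Power at 253 per arm is 0.801.
- Attrition: 506 / 0.90 = 562.2; the plan states 562.

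Only the standardised difference enters. The arithmetic is the same whichever SRDS score is analysed.

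**2. What the rule produces.** Nineteen questions, each contributing 0 or 1, give a maximum of 19 × 1 = 19. The SAP does not print this range; it is the natural reading of a sum of endorsements. The range of the volume score cannot be derived, because neither document gives the response format of the frequency part.

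**3. What the 12% requires.** If d = 0.25 equals a 12% difference in mean volume, then SD/mean = 0.12 / 0.25 = **0.48**. For a pure Poisson count SD/mean = 1/√mean, so 0.48 needs a mean of 1/0.48² = 4.3 offences in six months, and more if counts are over-dispersed. Since no mean or SD is given, the ratio is varied here as an assumption (normal approximation, 12% difference):

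| SD/mean | d | Power at 253 per arm | Total N for 80% |
|---|---|---|---|
| 0.48 | 0.25 | 80% | 504 |
| 1.0 | 0.12 | 27% | 2,182 |
| 2.0 | 0.06 | 10% | 8,722 |

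**4. Whether 12% carries over to the endorsement score.** An illustration under assumed inputs: 19 items with Poisson counts, gamma variation between persons (shape 1) and between items within a person (shape 0.5, 0.5 and 1), mean count per item 0.1, 0.3 and 0.5, and every rate cut by 12%. Volume falls by 12% in each case. The number of types endorsed falls by 10.1%, 8.1% and 7.6%. The standardised differences are close: 0.092, 0.102 and 0.110 for volume against 0.090, 0.098 and 0.104 for types. The percentage changes meaning between the scales, while power for a uniform reduction is similar.

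**5. Item count.** 18 × 2 = 36, so those two figures agree. Nineteen two-part questions would be 38. The conflict is 18 against 19.

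**6. The past-12-month window.** At month 6 it runs from six months before to six months after randomisation, so 6/12 = 50% precedes randomisation. At month 12 none does. If the month-6 total were built as SRDS0 + SRDS6 and analysed with the SAP's baseline covariate, adding SRDS0 to both sides of equation 1 gives

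SRDS0 + SRDS6 = α + β₁(allocation) + (β₂ + 1)(SRDS0) + the same remaining terms.

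β₁ and its standard error are unchanged. The outcome would be redundant with the primary one.

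**The case against.** The SAP's sentence begins with quantity, and one can argue that volume was meant and the rest is loose drafting. That may describe the intent, but the same sentence goes on to define quantity as summed endorsements, and nothing elsewhere corrects it.

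Three stronger readings are tempting, and the documents do not support them.

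- **That the trial is under-powered because of the scoring rule.** The sample size is set on a standardised 0.25 and holds for either score. Nor would moving to volume by itself secure the 12% target, which depends on SD/mean being about 0.48.
- **That two competing rules let the analyst choose after seeing the data.** There is only one operational rule, and the protocol defers to the SAP for the analysis. The fault is a mismatch with the stated outcome.
- **That the past-12-month outcome at month 6 costs power.** A dilution calculation gives a loss only for an unadjusted comparison. The SAP's outcome models all adjust for baseline, and this outcome has no equation or scoring rule of its own. It is a slip in the summary tables.

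It is also fair to say that the documents do not show the part-two responses to be free counts. If they are banded or capped, summing them does not directly give a number of offences.

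**Conclusion.** The contradiction is real and concerns the primary outcome. The SAP's rule yields an offence-type count, while the sample size sections, the summary tables and the protocol's Analysis section describe volume or number of offences. The primary analysis as written would estimate the wrong quantity relative to the trial's stated aim.

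The effect is on meaning: 506 and 562 stand. The 12% interpretation does not apply to the endorsement score, and for volume it rests on an unsupported SD/mean of about 0.48.

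This rests on reading the rule as 0 or 1 per question. The SD/mean range and the simulation are assumptions used to show scale. The 18-against-19 discrepancy is small but leaves the range of the score unfixed. The past-12-month entry at month 6 is minor.

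**What to change.** 1. Replace the scoring sentence in the SAP's Primary outcome analysis with the sum of the part-two frequency responses over the previous six months. State the response coding (including how any bands or caps become numbers) and the range. Name the number of items endorsed as a secondary outcome.
2. If the number of types is what is wanted as primary, keep the rule and instead change the sample size sections, the summary tables and the protocol's Analysis section.
3. Either way, support d = 0.25 on the chosen scale with a mean and SD.
4. Use one item count throughout.
5. Delete the past-12-month SRDS outcome at month 6 from both summary tables, and state the look-back period for the month-12 outcome in equation 2.

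Cost: mostly wording, done before any outcome analysis, plus finding a mean and SD. The 36-item entries suggest that frequencies are already collected at each visit. Because other sections say nineteen questions, this should be confirmed against the questionnaire in use.

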### **Secondary outcomes**

Emotional symptoms and behavioural difficulties will be assessed using the self-completed Strength and Difficulties questionnaire (SDQ; (Goodman, 1997)). This assesses behaviour across several domains including, conduct, hyperactivity, emotional regulation, peer relationships and prosocial behaviour and allows for the generation of two multi-component outcomes: internalising and externalising behaviours with the latter highly associated with current or future offending behaviour. We will assess total score, domain scores and multi-component scores. The outcome is widely used and has demonstrated excellent validity and moderate reliability in adolescent populations (Goodman, 2001). The SDQ is suitable for completion by those aged 10-17 years and those with mild learning disabilities (Law and Wolpert, 2014)

Wellbeing will be assessed using the Short Warwick-Edinburgh Mental Well-being scale (SWEMWBS; (Clarke et al., 2011)). SWEMWBS is a 7-item, self-completed scale addressing different aspects of eudemonic and hedonic mental health wellbeing. The scale is validated for adolescents and demonstrates good internal consistency (Ng Fat et al., 2017), and discriminant, construct and convergent validity (McKay and Andretta, 2017, Ng Fat et al., 2017).

Non-psychotic psychological health will be assessed using the General Health Questionnaire (GHQ12; (Goldberg and Hillier, 1979)), using norms derived for adolescent populations. This

12-item instrument has established validity and reliability in adolescent populations (Baksheev et al., 2011).

To assess the potential impact on the family environment we will assess family cohesion using the Brief Family Relationship Scale (BFRS; (Fok et al., 2014)), this 16-item instrument assesses family relationships, cohesion, and conflict, and has established convergent and discriminant validity.

We will use questions derived from a Client Service Receipt Inventory (CSRI;(Coulton et al., 2022)) to assess the frequency of school attendance, exclusions and suspensions, work status and criminal justice involvement over the previous 6-months. Client Service Receipt Inventory methods are an established and valid form of assessing participant resource use in randomised controlled trials and can be adapted for the target population (Knapp and Beecham, 1990).

All these outcomes will be assessed at baseline and then again at 6- and 12-month post-randomisation.

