The efficacy trial design is a mixed method, two level, individually randomised controlled trial of a trauma informed intervention, Trauma Recovery Model Relationship Building Together (RBT), versus business as usual (BAU) for adolescents and young adults served by Bridgend Youth Services (youth justice, edge of care, youth development and early help). There are two levels to the study randomisation. Level one involves selecting staff to be trained in RBT. This allocation is done for all staff, after baseline staff data collection, and is conducted by an on-line independent secure randomisation service, Sealed Envelope Ltd. Consent will be sought from all eligible staff prior to randomisation. As allocations are done at the same time and because we want to maximise balance across the groups on key parameters, we will employ minimisation for the allocation of staff. Our aim will be to maximise balance in terms of service (youth justice, edge of care, children's services, youth development, and early help) and speciality (specialised staff versus generic staff). Provision has been made to conduct a second wave of staff randomisation and TRM training if there is a high turnover of staff throughout the trial – a high turnover is one that exceeds 30%.

Level two allocation involves the randomisation of young people to RBT or BAU. This will be conducted by research staff, using a secure, on-line randomisation service (Sealed Envelope Ltd). after informed consent has been taken and the baseline assessment completed and before any trauma screening has been conducted. The allocation will involve an equal probability of receiving RBT or BAU and will employ random permuted blocks of variable size (4, 6 or 8) with a random block seeded throughout. Randomisation will be stratified by service (youth justice, edge of care, children's services, youth development and early help), sex (male, female), and age group (<15 years, 15 years or more). Stratification variables have been chosen to ensure allocation is balanced across services, sex, and age as some workers specialise in working with older or younger males and females.

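### The primary model (SAP eq. 1) and its 12-month counterpart (eq. 2) are valid but forgo some precision by leaving out the baseline SDQ externalising score

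*SAP*

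**What the plan says.** The SAP section on the primary outcome analysis specifies a linear analysis of covariance: "Models will be adjusted by baseline values, quantity of offences in the six months prior to randomisation and stratification factors". Eq. 1 lists allocation, baseline SRDS, sex, age and service dummies, and its key defines age as "age the age group", meaning under 15 versus 15 or over. Eq. 2 uses the same covariates for SRDS at 12 months. The protocol's Analysis section gives the same set: stratification covariates plus baseline SRDS.

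The protocol's Secondary outcomes section says the SDQ yields two composite scores, "internalising and externalising behaviours with the latter highly associated with current or future offending behaviour". It schedules the SDQ at baseline, 6 and 12 months, and the Randomisation section places the baseline assessment before allocation. The same Secondary outcomes section describes the SDQ as suitable for ages 10 to 17. The Participants section allows recruitment to age 21, in Youth Development only.

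Two other parts of the SAP bear on the point. Under Further analyses, the SDQ and age are candidate predictors of the primary outcome in an exploratory regression with selection at the 0.1 level. Under Imbalance at baseline, a further variable enters the analysis model if the groups differ on it by a large amount, and no threshold is given.

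**The concern.** A baseline variable that predicts the outcome beyond the covariates already in the model reduces residual variance, and so narrows the interval for the treatment effect. The protocol itself marks externalising score as such a candidate, and the trial pays to collect it from participants before allocation. The plan uses it in an exploratory model but not in the main comparison.

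The discretion it leaves also matters. As written, the score can reach the primary model only through the imbalance rule, which is applied after the groups have been compared at baseline and which does not define a large imbalance. Naming the covariate in advance removes that choice for a variable the protocol regards as related to offending.

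**Working it through.** **Inputs from the documents.** Effect size: "We have used an effect size difference of 0.25 as an important difference". Sample size: "using a two-sided test, alpha of 0.05 and power at 80% requires 506 young people to be followed-up", which is 253 per arm at 1:1 allocation. Loss to follow-up is 10%. No covariate credit is taken, and the SAP gives the reason: "There is no reliable literature on pre- and post-test correlations for the SRDS".

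**Inputs that must be assumed.** Neither document gives a correlation of SDQ externalising score, or of age, with SRDS at 6 months. Let r be the partial correlation of externalising score with 6-month SRDS after the eq. 1 covariates. I take r = 0.1, 0.2 and 0.3.

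**Step 1: reproduce the plan's figure.** A two-sample t calculation for 0.25 SD, two-sided 0.05 and 80% power gives 253 per arm, 506 in total, with power 80.1%. The normal approximation gives 252 per arm, and at 253 its power is 80.3%. Allowing for loss, 506 / 0.9 = 562.2, against 562 in the plan. The figure reproduces with no covariates.

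**Step 2: effect of the covariate on precision.** In a linear model the residual SD is multiplied by √(1 − r²), and the equivalent sample is 506 / (1 − r²).

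- r = 0.1: √0.99 = 0.995, so the SE falls 0.5%. 506 / 0.99 = 511, about 5 extra.
- r = 0.2: √0.96 = 0.980, so the SE falls 2.0%. 506 / 0.96 = 527, about 21 extra.
- r = 0.3: √0.91 = 0.954, so the SE falls 4.6%. 506 / 0.91 = 556, about 50 extra.

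**Step 3: effect on power.** Power = Φ(0.25 / (σ√(2/253)) − 1.96), with σ the residual SD. With no covariates σ = 1, and 0.25 / 0.0889 = 2.812, giving 80.3%. With σ = √(1 − r²), power is 80.7%, 81.9% and 83.8% for r = 0.1, 0.2 and 0.3. If eq. 1 already explained 25% of the variance (assumed), power would start at 90.1% and go to 90.4%, 91.2% and 92.6%.

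**Step 4: overlap with baseline SRDS.** Only association beyond baseline SRDS counts. Suppose baseline SRDS correlates 0.5 with the outcome and 0.5 with externalising score (both assumed). The partial correlation is then (a − 0.25) / 0.75, where a is the raw correlation of externalising score with the outcome. For a = 0.3, 0.4 and 0.5 this gives 0.07, 0.20 and 0.33. A moderate raw correlation can therefore leave little gain.

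**Step 5: age.** If ages were uniform over 10-17 or 10-21 (assumed), the split at 15 would keep 71% or 73% of the variance that linear age explains. For assumed age-outcome correlations of 0.1 to 0.4, linear age instead of the split lowers the SE by a further 0.1% to 2.6%.

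**Step 6: cost.** Eq. 1 has nine coefficients: intercept, allocation, baseline SRDS, sex, age group and four service dummies. On 506 that leaves 497 residual degrees of freedom. One more covariate leaves 496.

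**The case against.** The strongest reply is that nothing is broken. Baseline outcome plus stratification factors is a conventional set, the protocol and SAP agree on it, and the estimate and interval are valid without the score. That stands. A reader might infer that the trial is biased or short of its stated power without the covariate. The documents do not support this, because the 506 takes no covariate credit.

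A reader might also take the protocol to say that externalising score predicts future offending over and above past offending. It does not: its sentence covers current as well as future offending, and baseline SRDS already measures the preceding six months. Service dummies may absorb more. Nor does the SAP's remark on pre- and post-test correlations show baseline SRDS to be a weak covariate; it says that the correlation is unknown.

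It is tempting as well to count two-band age as a material loss. No passage says that age is prognostic within bands. The stated reason for stratifying on age is that some workers specialise by age and sex, and ages 18 to 21 occur only in one service, so the service term carries part of the range.

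The SDQ's stated age range is a fair practical objection and has to be met in the fix. Lastly, the SAP lets diagnostics decide the regression and the protocol expects a generalised linear model; the variance formula above is for the linear model, and gains under a count model would differ. None of these points shows harm from adding the score.

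**Conclusion.** The omission is a missed efficiency, not an error. Eq. 1 and eq. 2 are sound as they stand, and the stated 80% power does not rest on this change. Adding baseline externalising score would probably narrow the interval a little: a 0.5% to 4.6% smaller SE over assumed partial correlations of 0.1 to 0.3, and at most about 3.5 points of power from the planning base. The true gain cannot be determined from the documents and may lie at the low end because of overlap with baseline SRDS. The case for acting is that the data are already collected, the cost is close to nil, and a named covariate is better than one that may enter through an undefined imbalance rule. Age in years is a minor optional addition without documentary support.

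**What to change.** Before outcome data are seen:

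- Add baseline SDQ externalising score to eq. 1 and eq. 2, keeping baseline SRDS, service, sex and age group.
- Make the same change in the protocol's Analysis section. In the SAP's Missing data section, state that the score is in the imputation model whatever the variable-reduction screen shows.
- State that missing baseline scores are filled with the overall mean across both arms, so that no randomised participant is dropped for a missing covariate.
- State how ages 18 to 21 are handled given the protocol's 10-17 suitability statement; for example, use the score if collected, otherwise mean-fill with a missing indicator.
- Optionally, add age in years alongside age group.

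The cost is short matching edits in the two documents and about one degree of freedom, plus one each for a missing indicator or linear age if used. No new data are needed.
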